4.2.2.1.2 Maximum Overall Intensity

Maximum overall intensity is derived from the daily intensities computed as described in Section 4.2.2.1.1 and is calculated as the maximum of the daily intensities over the period considered.

Note: The maximum intensity could be considered "None" (not a reaction) in the analysis despite being considered a reaction by the investigator (eg, swelling measurement > 0 mm but < 25 mm in adults).

4.2.2.1.3 **Presence**

Presence is derived from the maximum overall intensity over the time period considered:

- None: No presence
- Grade 1, Grade 2, or Grade 3: Presence
- Missing or Unknown: Missing presence

Participants with at least one non-missing presence for a specific endpoint will be included in the analysis. Conversely, those without a non-missing presence will not be included in the analysis of the endpoint.

The time period is displayed as follows:

- Injection site reactions: D1-D4, D5-D8, D9 or later
- Systemic reactions: D1-D4, D5-D8, D9-D15, D16 or later.

4.2.2.1.4 Time of Onset

Time of onset is derived from the daily intensities computed as described in Section 4.2.2.1.1. It corresponds to the first day with intensity of Grade 1, Grade 2, or Grade 3.

Note: If a reaction is not continuous (ie, reaction occurs over two separate periods of time intervened by at least one daily intensity Missing or None) then the time of onset is the first day of the first occurrence.

Time of onset period is displayed as follows:

- Injection site reactions: D1-D4, D5-D8
- Systemic reactions: D1-D4, D5-D8, D9-D15.

4.2.2.1.5 Number of Days of Occurrence During the Solicited Period

Number of days of occurrence over the period considered is derived from the daily intensities computed as described in Section 4.2.2.1.1. It corresponds to the number of days with daily intensities of Grade 1, Grade 2, or Grade 3. Number of days of presence on the solicited period with a specified intensity may also be derived.

Number of days of occurrence during the solicited period will be displayed by categories as follows:

- Injection site reactions: 1-3 days, 4-7 days, 8 days
- Systemic reactions: 1-3 days, 4-7 days, 8-14 days, 15 days

4.2.2.1.6 Overall Number of Days of Occurrence

If a reaction is ongoing at the end of the solicited period, then the overall number of days of occurrence is derived from the daily intensities and the end date of the reaction after the end of the solicited period. The overall number of days of presence is:

• (End date - investigational vaccination date) + (number of days of presence within the solicited period) - length of the solicited period + 1

If the end date is missing or incomplete (contains missing data), the overall number of days of presence will be considered as Missing.

Overall number of days of occurrence will be displayed by category (range) as follows:

- Injection site reactions: 2-3 days, 4-7 days, 8 days or more, missing end date
- Systemic reactions: 2-3 days, 4-7 days, 8-14 days, 15 days or more, missing end date

4.2.2.1.7 Ongoing

Ongoing is derived from the last daily intensity of the solicited period computed as described in Section 4.2.2.1.1 and the maximum intensity on the ongoing period. The investigator's ongoing flag is not used because the measurement would determine the ongoing status of the reaction.

- Ongoing: if the last daily intensity of the solicited period is at least Grade 1 and the maximum intensity on the ongoing period is at least Grade 1
- Not ongoing: if the last daily intensity of the solicited period is None or the maximum intensity on the ongoing period is None.
- Missing: all other conditions (in this case, it is not included in the denominator of the ongoing analysis in the safety tables).

4.2.2.2 Unsolicited AEs

4.2.2.2.1 **Presence**

An observation will be considered an event if it has at least a verbatim term and is not a Grade 0 intensity event.

Grade 0 events will be not included in safety analysis but will be included in separate listings.

4.2.2.2.2 Intensity

Intensity will be derived according to the following classification: None, Grade 1, Grade 2, Grade 3, or Missing.

If the unsolicited AE is measurable and its preferred term is part of the list of solicited reactions, then the measurement is derived based upon and following the same rule of the intensity scales defined in the protocol for that measurable injection site or systemic reaction. Note the intensity could be considered as "None" (not a reaction) in the analysis despite being considered a reaction by the investigator (eg, swelling measurement > 0 mm but < 25 mm in adults).

Intensity for the other unsolicited AEs will correspond to the value reported in the CRF.

The maximum intensity corresponds to the highest intensity for a unique term.

4.2.2.2.3 Last Vaccination

Last vaccination before an unsolicited AE is derived from the start date of the unsolicited AE provided in the CRF and is calculated as follows:

• If an unsolicited AE has a complete start date and different to any of the vaccination dates, the start date is used to determine the last vaccination before the unsolicited AE

If the start date is missing or partially missing, or equal to any vaccination date, then the visit number in the "Appeared after Visit" or similar field, is used to determine the last vaccination before the unsolicited AE.

4.2.2.2.4 Time of Onset

Time of onset is derived from the start date of the unsolicited AE and the date of last vaccination as described in Section 4.2.2.1.1:

Time of Onset = start date of the unsolicited AE - date of last vaccination before the unsolicited AE + 1.

The time of onset is considered as missing only if one or both dates are missing or partially missing.

The unsolicited AEs will be analyzed "Within 28 days" after each vaccination, which corresponds to AEs with a time of onset between 1 and 29 days. An AE with missing time of onset will be

considered to have occurred just after the last vaccination (computed according to the Section 4.2.2.2.4), so will be included in these tables.

Time of onset period is displayed as D1-D4, D5-D8, D9-D15, D16 or later, and Missing.

Note: Unsolicited AE that occurred before vaccination (negative time of onset) or with a time of onset higher than defined above will not be included in analysis but will be listed separately.

4.2.2.2.5 **Duration**

Duration is derived from the start and end dates of the unsolicited AE:

Duration = End date of unsolicited AE - start date of unsolicited AE + 1.

The duration is considered as missing only if one or both the start and end dates of the unsolicited AE is missing or partially missing.

Duration will be displayed by categories as 1-3 days, 4-7 days, 8-14 days, 15 days or more, missing.

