4.2.2.4 SAEs

An event will be considered as a serious event if "Yes" is checked for "Serious" in the CRF.

SAEs will be analyzed throughout the study using the following periods:

- Within 28 days after a vaccination
- During the period from 29 days after the vaccination until the last participant contact at M6
- During the study for related SAEs (ie, all related SAEs occurred during the study)

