4.2.2.7.6 Adverse Events Leading to Study Discontinuation

This information will be summarized as collected. A flag is available in the clinical database for all AEs in order to identify AEs leading to discontinuation before the end of active phase.

In general, the items that are counted are:

- Disposition table: A participant who, on the "Completion at End of Study" form question "What was the participant's status?" has "Adverse Event" checked.
- Safety overview table: A participant who has either on the "Completion at End of Study" form, question" What was the participant's status?" has "Adverse Event" checked or lists a solicited AE that has "Caused Study Termination" checked that is at least Grade 1 or an unsolicited AE that has "Caused Study Discontinuation" checked that is at least Grade 1 or missing and is within the time period indicated.

System Organ Class (SOC)/Preferred Term (PT) table: A solicited AE that has "Caused Study Termination" checked that is at least Grade 1 or an unsolicited AE that has "Caused Study Discontinuation" checked that is at least Grade 1 or missing and is within the time period indicated.

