5.3.2.5 Start Date and Stop Date

Missing or partially missing start dates or end dates for unsolicited AEs (including SAEs) will remain missing and not be imputed. If the start date is missing or partially missing, the time of onset will be considered to be missing. Nevertheless, unsolicited AEs with missing time of onset will be included in analyses according to the last vaccination (computed according to the Section 4.2.2.2.3). If either the start date or end date is missing or partially missing, the duration will be considered missing.

Missing or partially missing end dates for ongoing solicited AEs will remain missing and not be imputed.

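### The onset rule counts an SAE or AESI with a partial start date as within 28 days, even when its known month or visit shows a later start

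*SAP*

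**What the plan says.** - **Onset (SAP 4.2.2.2.4).** The formula is "Time of Onset = start date of the unsolicited AE - date of last vaccination before the unsolicited AE + 1", and the 28-day window is onset day 1 to 29. "The time of onset is considered as missing only if one or both dates are missing or partially missing", so a known month and year is treated like no date at all. An AE with missing onset is "considered to have occurred just after the last vaccination (computed according to the Section 4.2.2.2.4), so will be included in these tables".
- **Visit field (SAP 4.2.2.2.3).** When the start date is missing or partial, the visit recorded under 'Appeared after Visit' "is used to determine the last vaccination before the unsolicited AE". No other use is given. Protocol 7.1 confirms a single vaccination.
- **Missing dates (SAP 5.3.2.5).** "Missing or partially missing start dates or end dates for unsolicited AEs (including SAEs) will remain missing and not be imputed". It adds that "unsolicited AEs with missing time of onset will be included in analyses according to the last vaccination".
- **SAEs and AESIs.** SAP 4.2.2 defines an SAE as a type of unsolicited AE, and protocol Table 3.1 counts AESIs among unsolicited AEs. The second SAE analysis period in SAP 4.2.2.4 is "During the period from 29 days after the vaccination until the last participant contact at M6". SAP 4.2.2.5 has the matching period for AESIs. Neither section has its own rule for incomplete dates.
- **Collection (protocol 8.3.1).** Non-serious unsolicited AEs are collected to D29, SAEs and AESIs to Month 6, and related SAEs and deaths to Year 5.

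**The concern.** A default that places an undated event early is a common and cautious choice. This rule goes further and overrides information already in the database. An SAE recorded as starting in June, after a January vaccination, has a month that excludes the first 28 days, yet it is counted there. The visit field could settle many such cases, but with one vaccination it always returns D01.

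The 28-day window matters in this trial. Protocol Table 2.1 names it as the observation period for early detection of viscerotropic and neurotropic disease, and SAP Table 7.8 reports SAEs, deaths and AESIs within it. These events are expected to be rare, so a single misplaced one changes a row visibly. Moving a late event forward is also not cautious in every respect. It can take the event out of the 29-day-to-M6 row, and in the comparator arm it makes vYF look relatively better in the early window.

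**Working it through.** **1. Reproduce the window.** Onset = start date − vaccination date + 1. The vaccination day gives 0 + 1 = 1, and 28 days later gives 28 + 1 = 29. This matches the stated window of 1 to 29. A start 29 days after vaccination gives 30, so the next period begins where this one ends.

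**2. Follow a partial date through the rules.** A partial start date makes onset missing (4.2.2.2.4). The visit field then selects the last vaccination, which is D01 (4.2.2.2.3; protocol 7.1). The event enters the 28-day tables (4.2.2.2.4; 5.3.2.5). The only exclusion of late events in 4.2.2.2.4 requires a computed onset above 29, and none exists here.

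**3. Ask what the known part of the date allows.** Take the earliest day compatible with the partial date. With an assumed vaccination date of 15 January 2022:

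| Recorded start | Earliest possible onset day | SAP placement |
|---|---|---|
| June 2022 | 137 + 1 = 138 | within 28 days |
| March 2024 | 776 + 1 = 777 | within 28 days |
| 2025 | 1082 + 1 = 1083 | within 28 days |

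The last two could be collected only as related or fatal SAEs.

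Running through all 365 vaccination dates in 2022, a start month one calendar month later has an earliest onset between day 2 and day 32, so it is usually ambiguous. A start month two calendar months later has an earliest onset between day 30 and day 63, so it is never inside the window. Real ambiguity is confined to the vaccination month, most cases of the following month, and year-only dates that overlap the window.

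**4. Ask what the visit field allows.** Protocol Table 8.1 puts Visit 5 at D180 ± 15 days. An event that appeared after Visit 5 therefore starts at about day 180 − 15 = 165 or later. Visit 4 is planned for D29 or later, so an event after Visit 4 is outside the window unless the visit fell on D29 and the event began the same day.

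**5. Size of one misplaced event.** These are exact (Clopper-Pearson) 95% intervals, the SAP's method, using the planned group sizes of 380 and 190 (SAP 5.5). For zero events the upper limit is 1 − 0.025^(1/n).

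| Events | vYF, n = 380 | YF-VAX, n = 190 |
|---|---|---|
| 0 | 0% (0 to 0.97%) | 0% (0 to 1.92%) |
| 1 | 0.26% (0.01 to 1.46%) | 0.53% (0.01 to 2.90%) |
| 2 | 0.53% (0.06 to 1.89%) | 1.05% (0.13 to 3.75%) |

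**The case against.** The strongest reply is that the reach is short and the convention is cautious. Much of this stands.

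- Non-serious AEs that are not AESIs are collected only to D29, so they cannot be misplaced by months. After Month 6 only related SAEs and deaths are collected.
- SAEs are reported within 24 hours of awareness and reconciled with the pharmacovigilance database, and data are reviewed before lock (protocol 8.3.1; SAP 4.2.2 and 5.6). Persistent partial dates should be few, though none of these steps guarantees a complete date.
- The onset display has a Missing category, so such events can be seen there. They still count in the 28-day totals.
- Safety is descriptive and both arms follow the same rule. Suspected viscerotropic and neurotropic disease is assessed against case definitions (protocol 8.3.6 and 10.3.6), not from Table 7.8.
- For a wholly undated event, early placement is reasonable. It does not justify discarding a known month or visit.

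A reader might infer that long-term rates are understated. The documents do not support this. The SAP has no onset period after Month 6, and the whole-study rows in Table 7.8 are cumulative, so they count the event wherever its onset is placed.

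A reader might also infer that a Year 3 event would distort the 28-day results when they are first reported. It cannot. The first interim analysis covers safety to D29 according to SAP 5.7, or to Month 6 according to SAP 5.4, and both precede Year 3. Such an event matters only if the 28-day tables are regenerated later. Under the SAP 5.7 cut-off, the same condition applies to events between D29 and Month 6.

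**Conclusion.** The point holds in a limited form. As written, the rules place a post-vaccination SAE or AESI with a partial or missing start date in the 28-day tables, even when its month, year or visit shows onset after D29. The 28-day rows of Table 7.8 can only gain from this, and the 29-day-to-M6 rows can lose. The primary endpoint is not touched.

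One event shifts a zero row to 0.26% in vYF or 0.53% in YF-VAX. This rests on the planned denominators. SAP 5.7 says the planned sample size was unlikely to be reached, and smaller groups would make each shift slightly larger. The number of partial dates is not stated. For deaths, it is assumed that the 28-day row follows the onset of the fatal event, since the SAP gives no separate rule.

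A reader of SAP 4.2.2.7.6 might infer a related fault: that the discontinuation row has no time limit for the end-of-study form, because the limit follows only the last clause ("at least Grade 1 or missing and is within the time period indicated"). That rests on one parsing. The closing words can govern the whole list, and Table 7.8 already puts the row under its 28-day heading. It is an ambiguity of wording, not a shown error, and is not part of this point.

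**What to change.** In SAP 4.2.2.2.4 and 5.3.2.5, replace the blanket default with a rule on these lines:

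- When the start date is partial or missing, use the known month and year together with the 'Appeared after Visit' value and the actual date of that visit.
- If these show onset after D29, leave the event out of the 28-day tables. Count it in the 29-day-to-M6 period where it falls there, and otherwise only in the whole-study rows.
- Keep the default to within 28 days only when the available information is compatible with onset day 1 to 29.

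Correct the cross-references in the same edit. For the last vaccination, SAP 4.2.2.2.4 cites itself where 5.3.2.5 cites 4.2.2.2.3. It also cites 4.2.2.1.1, which is Daily Intensity, for the date of last vaccination.

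The cost is two or three sentences and a small change to the onset derivation. The fields are already collected. The change should be in place before the next lock from which Table 7.8 is produced.

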4.2.2.3 Medically-Attended Adverse Event

An event will be considered as an MAAE if "Yes" is checked for "Is the event an MAAE?" in the CRF.

MAAE will be analyzed during the following time periods:

- Within 28 days after a vaccination
- During the period from 29 days after the vaccination up to M6 post-vaccination as part of the SAE (Serious MAAE) and at any time during the study as part of SAEs that are related or fatal (serious related or fatal MAAE)

4.2.2.4 SAEs

An event will be considered as a serious event if "Yes" is checked for "Serious" in the CRF.

SAEs will be analyzed throughout the study using the following periods:

- Within 28 days after a vaccination
- During the period from 29 days after the vaccination until the last participant contact at M6
- During the study for related SAEs (ie, all related SAEs occurred during the study)

4.2.2.5 Adverse Events of Special Interest

An event will be considered as an AESI if "Yes' is checked for "Is the event an AESI?" in the CRF.

AESIs will be analyzed throughout the study using the following periods:

- Within 28 days after a vaccination
- During the period from 29 days after the injection until the last participant contact at M6

4.2.2.6 Biological Safety Tests

The evaluation of biological safety parameters will consist in assessing whether each parameter is within or outside normal range and depending on the parameters, according to severity. Normal ranges for each biological parameter will be provided by the study centers and will be displayed in the listings. Biological safety endpoints will be assessed on whether or not they reach the predefined intensity thresholds. The pre-defined intensity thresholds are shown in Table 4.1.

Laboratory Endpoint	Unit	Grade 1	Grade 2	Grade 3
Creatinine	mg/dL	1.5 - 1.7	1.8 - 2.0	> 2.0
СРК	mg/dL	1.25 – 1.5 x ULN	1.6 – 3.0 x ULN	> 3.0 x ULN
Alkaline phosphate –		1.1 – 2.0 x ULN	2.1 – 3.0 x ULN	> 3.0 x ULN
increase by factor				
Liver Function Tests –				
ALT, AST increase by		> 1.1 – 2.5 x ULN	2.6 - 5.0 x ULN	\geq 5.0 x ULN
factor				
Bilirubin – when		1.1 – 1.25 x ULN	1.26 – 1.5 x ULN	> 1.5 x ULN
accompanied by any				
increase in Liver				
Function Test, increase				
by factor				
Bilirubin – when Liver		1.1 – 1.5 x ULN	1.6 - 2.0 x ULN	> 2.0 x ULN
Function Test is				
normal; increase by				
factor				
Hemoglobin (Female)	gm/dL	11.0 - 12.0	9.5 - 10.9	< 9.5
Hemoglobin (Female)		Any decrease – 1.5	1.6 - 2.0	> 2.0
change from baseline	gm/dL			
value				
Hemoglobin (Male)	gm/dL	12.5 - 13.5	10.5 - 12.4	< 10.5
Hemoglobin (Male)		Any decrease – 1.5	1.6 - 2.0	> 2.0
change from baseline	gm/dL			
value				
WBC Increase	cell/mm ³	$10\ 800-15\ 000$	$15\ 001-20\ 000$	> 20 000
Decrease in WPC	cells /	2 500 2 500	1 500 2 400	< 1.500
Declease III wBC	mm ³	$2\ 500 = 5\ 500$	1 300 - 2 499	< 1 300
Decrease in	cells /	750 1 000	500 740	< 500
Lymphocytes	mm ³	/30 - 1 000	500 - 749	< 300
Decrease in Neutronhile	cells /	1 500 2 000	1 000 1 400	< 1.000
Decrease in Neurophils	mm ³	1 300 - 2 000	1 000 = 1 499	< 1 000
Decrease in Platelets	cells /	125 000 - 140 000	100 000 - 124 000	< 100 000
	mm ³	123 000 - 140 000	100 000 - 124 000	× 100 000
Eosinophils	cell/mm ³	$650 - 1\ 500$	$1\ 501-5\ 000$	> 5 000

Table 4.1: Intensity grading scale for laboratories abnormalities

ULN: Upper Limit of Normal

LLN: Lower Limit of Normal

WBC: white blood cell

ALT: alanine aminotransferase

AST: aspartate transaminase

4.2.2.7 Other Safety Endpoints

4.2.2.7.1 Pregnancy

This information will not be included in the analysis but will be listed separately. No derivation or imputation will be done.

4.2.2.7.2 Action Taken

This information will be summarized as collected, including missing observations. No derivation or imputation will be done.

4.2.2.7.3 Seriousness

This information will be summarized as collected. No derivation or imputation will be done.

4.2.2.7.4 Outcome

This information will be summarized as collected. No derivation or imputation will be done.

4.2.2.7.5 Causal Relationship

This information will be summarized as collected in the field "Relationship to study vaccine". Missing causal relationship will be handled as described in Section 5.3.2.2. Relationship to study procedure is only presented in the listing.

4.2.2.7.6 Adverse Events Leading to Study Discontinuation

This information will be summarized as collected. A flag is available in the clinical database for all AEs in order to identify AEs leading to discontinuation before the end of active phase.

In general, the items that are counted are:

- Disposition table: A participant who, on the "Completion at End of Study" form question "What was the participant's status?" has "Adverse Event" checked.
- Safety overview table: A participant who has either on the "Completion at End of Study" form, question" What was the participant's status?" has "Adverse Event" checked or lists a solicited AE that has "Caused Study Termination" checked that is at least Grade 1 or an unsolicited AE that has "Caused Study Discontinuation" checked that is at least Grade 1 or missing and is within the time period indicated.

System Organ Class (SOC)/Preferred Term (PT) table: A solicited AE that has "Caused Study Termination" checked that is at least Grade 1 or an unsolicited AE that has "Caused Study Discontinuation" checked that is at least Grade 1 or missing and is within the time period indicated.

4.2.3 Derived Other Variables

4.2.3.1 Age for Demographics

Considering the Sanofi convention of date of birth collection, the age of a participant at the date of informed consent signature/visit 1 will be entered in the electronical CRF.

4.2.3.2 Duration of the Study

The durations are computed in days as follows:

Latest date of all participants (termination date, last visit date, date of last contact) - earliest date of all participants (date of visit V01) + 1.

where $(y_1, y_2, ..., y_n)$ are the observed titers or other data where applicable for each participant. Rounding rules on descriptive statistics will follow the Sanofi Pasteur standard technical guideline ("Conventions for the Presentation of Descriptive Statistics").

